### **9.1.2 Assessment, Reporting and Monitoring of Adverse and Serious Adverse Events**

AEs and SAEs will be elicited by research assistants at each assessment (baseline through follow up). The RA will ask the subject whether she has experienced any new problems or a worsening of existing problems since her last assessment using the AE Worksheet. The RA should be focused on gathering data to aid the Study Clinician in determining study relatedness. Assessment of depression must include an assessment of suicidal ideation, as suicidal ideation may require immediate clinical assistance and qualify as an SAE. All clinically significant AEs will be captured on a standardized AE Log, with immediate assessment for whether or not the AE is serious, and whether or not the AE is study-related, in consultation with the site coordinator or Study Clinician (PhD, MD, PI). Study-relatedness will ultimately be determined by the Study Clinician following discussion with the staff member reporting the AE. AEs that are not serious or study related do not require any further paperwork documentation besides the AE Log. AEs and SAEs could also be spontaneously disclosed by the subject during intervention sessions. In this case, the therapist will record and report them, as described here.

Study staff will be trained to provide crisis intervention and referral for clinical emergency situations. Standard CTP procedures for handling crisis situations should be used. The Site Coordinator and/or Study Clinician will be available by beeper (or other similar method), within 24-hours for consultation and crisis intervention for problems.

From baseline informed consent discussion onward, subjects are advised that conversation about HIV or STDs, introduction of (male or female) condoms or other methods of protection, safer sex negotiation, refusal of unprotected sex, or, even their participation in a women's intervention may anger their male partners. This anger may put them at risk for emotional, physical and/or sexual abuse. Subjects are also advised that emotional distress could develop or increase in response to these problems. For this reason, subjects are advised to observe any signs of such anger in their partners, or such problems in themselves, and to discuss them with study staff immediately. In addition, study assessments contain modules concerning abuse, which can alert the study staff to evolving risk.

All study related AEs and SAEs will be followed until resolution. Monitoring and reporting of SAEs will be maintained by the: CTP staff members (e.g. research assistants, therapists, etc.); CTP Site Coordinator; Protocol PI; Study Project Manager; Lead Investigator; and NIDA Medical Monitor.

Figure 3 presents a flow chart for AE and SAE reporting. Only SAEs and related AEs will be recorded and entered into the study database (via the AE CRF). All SAEs will be recorded on the AE CRF, the SAE Form, and a summary narrative provided via the SAE Summary Report. The AE CRF is a form that will be used to document any adverse event that is thought to be serious or study related. The AE CRF is completed at each assessment point and on an as needed basis. If the adverse event is found to be serious, then a SAE Form and SAE Summary Report must be completed. The SAE Form should be completed by or in consultation with the Study Clinician. The SAE Summary Report contains demographic information and an event narrative and should be completed by the Study Clinician.

All SAEs must be reported by fax of the AE CRF, within 24 hours to the Lead Investigator, Protocol PI, Node PI, NIDA Medical Monitor, and to IRBs in accordance with their guidelines. The Study Clinician will be responsible for reviewing the AE CRF and SAE Form, querying the staff as needed, and completing an SAE Summary Report, to be co-signed by the Lead Investigator. Within 14 days, the AE CRF and the SAE Form and the signed SAE Case Summary are forwarded to the NIDA Medical Monitor, Protocol PI, and Node PI. At the same time, reports will be submitted to all involved IRBs per reporting requirements.

All study staff – including research assistants, therapists, CTP Site Coordinator, Protocol PI, Lead Investigator, and Study Project Manager, will receive common training for AE and SAE detection, monitoring and reporting. Training will include: definition of AEs; definition and grading of SAEs; indications and procedures for completing the AE log; indications and procedures for completing AE CRFs; indications and procedures for completing SAE Forms and SAE Summary Reports; and procedures for reporting SAEs.

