## **6.0 Study Treatments**

### **6.1 Study Therapies**

There are two intervention conditions in the proposed study: 1) five-session SSB group; and 2) a single standard-of-care HIV education session, serving as a comparison condition. Both interventions will be carried out by CTP female drug treatment counselors who receive approximately 20 hours of training. In [name]'s and Schilling's

studies, skills building intervention training required 20 hours. Both interventions are manual-driven. These two features will make ongoing technology transfer to the CTPs highly likely. The HE condition consists of one approximately 60-minute session, while the SSB will consist of 5 approximately 90-minute groups. Each condition will consist of 3-8 women. Each intervention condition will be run by two female co-leaders.

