### **6.1.1 HIV Education (HE)**

This intervention will consist of the HIV information covered in the first session of the SSB intervention using discussion, flip chart visual materials and informational and resource handouts. This will be an approximately 60 minute group session covering: HIV definitions, transmission, testing and counseling, treatment, and prevention. Certificates will be distributed at the end of the session. Participants will be paid for their attendance to the treatment groups. Reasonable and non-coercive reimbursement sums will be determined on a site-by-site basis. Women will be paid in cash or vouchers (as determined by the CTP) for their participation. It is recommended that participants are paid only if they attend the majority of the session (40 minutes), although the decision to do this may vary based on local IRBs. Paying participants to attend treatment sessions calls into question the issue of sustainability. In the CTPs, patients are not paid to attend sessions. The current protocol is voluntary research. It is the investigators' experience that it is difficult to attract a wide distribution of patients at voluntary sessions without monetary incentives. If the SSB intervention proves efficacious, then CTPs could make it a mandated part of treatment and, thus, eliminate the need for incentives.

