### **6.1.2 Safer Sexual Skills Building (SSB)**

This intervention will consist of 5 approximately 90-minute group sessions. Participants will be paid for their attendance to the treatment groups in cash or vouchers. Reasonable and non-coercive reimbursement sums will be determined on a site-by-site basis. It is recommended that participants are paid only if they attend the majority of the session (60 minutes), although the decision to do this may vary based on local IRBs.

Primarily through active problem-solving, behavioral modeling, role play rehearsal, interval practice, troubleshooting, and peer feedback and support, this intervention will build cognitive, affective and behavioral skills for safer sexual decision making and behavior. The 5 sessions entail:

- 1)** Using discussion, flipchart visual materials, and informational and resource handout materials, the counselor will conduct a 90 minute session covering: HIV/STD definitions, transmission, testing and counseling, treatment, and prevention.
- 2)** Using discussion, flipchart visual materials, risk vignettes, and risk assessment worksheets, women will assess their own personal risk for HIV/STDs. Using discussion, flipchart visual materials, HIV sexual risk behavior and alcohol and drug use vignettes and triggers assessment worksheets, women will identify the internal and external triggers to HIV sexual risk behavior. Particular emphasis will be placed on the role of (1) partner pressure, threat and abuse; and (2) alcohol and drug use effects. Women will also identify sources of support for safer sexual behavior and ways of seeking their help.
- 3)** Using discussion, flipchart visual materials, and male and female genital models, women will: a) observe male and female condom handling, insertion and removal; b) rehearse these skills; and c) give feedback about these methods. Women will use the SODAS (stop; options; decide; action; self-praise) problem-solving model to brainstorm constructive responses to HIV sexual risk and drug use vignettes. Women will identify

adverse effects posed by safer sexual behavior and negotiation for them. Particular emphasis will be placed on risk of partner violence, sexual abuse and verbal abuse, relationship break-up, and relationship strain.

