**4)** Using safer sexual behavior and safer sexual negotiation vignettes women will: a) observe behavioral modeling of a range of action options including planned passivity, cajoling, assertiveness, frank withdrawal and other options; b) brainstorm pros and cons of these options; c) problem-solve courses of action for these options; and d) rehearse these skills in role plays. Women will identify adverse effects posed by safer sexual behavior and negotiation for them. Particular emphasis will be placed on risk of partner violence, sexual abuse and verbal abuse, relationship break-up, and relationship strain.

**5)** Using flipchart visual materials and “take home message” worksheets, women will wrap up and summarize the major action options they have identified during the intervention. Through the use of unsafe sexual behavior vignettes, women will become familiar with cognitive-behavioral techniques for “breaking” drug and alcohol use and/or unsafe sexual behavior slips before they become full-blown relapses. Resource handouts, especially for dealing with partner violence, seeking HIV/STD testing and counseling, and seeking women’s activism organizations will be reviewed. A graduation ceremony will be held, and certificates will be given.

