### 11.7 Analysis of Safety Measures

For each individual adverse experience, each participant will be categorized by the maximal severity reported during the intervention phase. Adverse experiences occurring during screening but ending prior to randomization, or those starting during screening and continuing into the randomization phase with the same or less severity will be excluded. The severity categories are: none (if the participant never had the adverse experience), mild, moderate, severe, life threatening and lethal. If a participant has an adverse experience more than once, then the adverse effect with most severe rating will be used in the analysis. It may be necessary to group the individual adverse experiences before any analysis can be performed. If this is necessary, then the coding will be performed centrally by Long Island node personnel.

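### Recorded adverse events can be inflated in the SSB arm, because therapists also report events disclosed in session and SSB has five sessions against one in HE

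*Protocol*

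**What the plan says.** **Common route.** Sections 8.5 and 9.1.2 have the research assistant complete an AE Worksheet at baseline, immediately post-intervention, and at 3 and 6 months. It holds one general question and a follow-up question, and asks about problems since the last assessment. Visit times are counted from the first treatment session in both arms (Study Flow Chart).

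**Session route.** Section 9.1.2 adds: "AEs and SAEs could also be spontaneously disclosed by the subject during intervention sessions". It continues: "In this case, the therapist will record and report them, as described here".

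**Session contact.** Section 6.1: "The HE condition consists of one approximately 60-minute session, while the SSB will consist of 5 approximately 90-minute groups".

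**Session content.** For HE, section 6.1.1 says: "This intervention will consist of the HIV information covered in the first session of the SSB intervention". In that SSB session, "the counselor will conduct a 90 minute session covering: HIV/STD definitions, transmission, testing and counseling, treatment, and prevention" (6.1.2). For SSB session 2 the text reads "Particular emphasis will be placed on the role of (1) partner pressure, threat and abuse", and for sessions 3 and 4 "Particular emphasis will be placed on risk of partner violence, sexual abuse and verbal abuse, relationship break-up, and relationship strain". Session 5 is a wrap-up that includes resource handouts on partner violence.

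**Safety summary.** Section 11.7: "each participant will be categorized by the maximal severity reported during the intervention phase". It makes no distinction by source of report.

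**The concern.** Abusive partner behavior and marked emotional distress are the harms the protocol itself foresees (8.5, 9.1.1). They are also what SSB sessions 2 to 4 invite women to talk about. An event that follows the single HE session cannot enter the record through a later study session, whereas SSB has four more. The unequal contact falls within the period that 11.7 summarises.

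Classification may be affected too. Only SAEs and study-related AEs enter the database, and relatedness is settled after discussion with the staff member who reported the event (9.1.2). On the session route that person is an unblinded therapist (6.3.2).

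What is at stake is interpretation. SSB could truly provoke partner anger, so an excess in SSB could be real, an artefact of reporting, or both. Without the source of each event, no later analysis can separate these.

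**Working it through.** The protocol states no adverse event rate and no safety power, so there is no figure of its own to reproduce.

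**Contact, from 6.1**
- SSB: 5 × 90 = 450 minutes. HE: 1 × 60 = 60 minutes. Ratio 450/60 = 7.5.
- Sessions after the first: 4 in SSB, 0 in HE.
- Worksheet assessments after randomization: 3 in each arm.
- Sessions with stated emphasis on partner threat, violence or abuse: 3 in SSB (sessions 2, 3 and 4), 0 in HE.

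**Illustration A: the event is present throughout the session period.** Let w be the chance that the worksheet detects it and h the chance of disclosure at each session, independently, with n sessions attended. Detection = 1 − (1 − w)(1 − h)^n, with n = 5 in SSB and n = 1 in HE. The true rates are equal. Both w and h are assumptions.
- w = 0.9, h = 0.05: (1 − 0.1 × 0.95^5)/(1 − 0.1 × 0.95) = 0.923/0.905 = 1.02.
- w = 0.5, h = 0.20: (1 − 0.5 × 0.8^5)/(1 − 0.5 × 0.8) = 0.836/0.600 = 1.39.
- Session route alone at h = 0.10: 1 − 0.9^5 = 0.41 in SSB against 0.10 in HE.

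**Illustration B: the event arises after session 1.** HE has no session left and SSB has k = 2 or 4. Ratio = [1 − (1 − w)(1 − h)^k]/w.
- w = 0.9, h = 0.05, k = 2: (1 − 0.1 × 0.9025)/0.9 = 1.01.
- w = 0.5, h = 0.20, k = 4: (1 − 0.5 × 0.4096)/0.5 = 1.59.

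Recorded SSB:HE ratio with equal true rates, h from 0.05 to 0.20:

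| Worksheet detection w | A | B (k = 2 to 4) |
|---|---|---|
| 1.0 | 1.00 | 1.00 |
| 0.9 | 1.02–1.05 | 1.01–1.07 |
| 0.7 | 1.07–1.19 | 1.04–1.25 |
| 0.5 | 1.17–1.39 | 1.10–1.59 |

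**Chance of a nominally significant SSB excess under B.** Take 240 per arm, an assumed 10% true rate, and ignore clustering; the reference in one direction is 2.5%. With w = 0.5, h = 0.20, k = 4, recorded rates are 10% × 0.795 = 7.95% against 10% × 0.5 = 5.0%, and the chance is about 26%. With w = 0.9 and h = 0.05 it is about 3%.

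**Abuse assessment.** Section 8.5 says that all study assessments contain abuse modules. Table 2 schedules the abuse experience assessment at baseline, 3 months and 6 months, and not at the immediate post-intervention visit. If Table 2 is what happens, the worksheet's general question is the main common check for partner abuse at that visit, which makes w below 1 more plausible there.

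**The case against.** The strongest reply is that both arms get the same question on the same schedule, covering everything since the last assessment. A session disclosure adds to the count only if the worksheet would have missed the event. That stands, and it is why the effect may be nil.

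HE women also have other routes. Participants in both arms are told to raise partner anger or distress with study staff at once (9.1.2). Therapists come from the programs' own counseling staff (6.2), and section 7.2 foresees individual sessions during the trial. The illustrations give these routes no weight, and they assume full SSB attendance and independent disclosures. They show direction and possibility, not size.

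Section 11.7 describes a categorisation and states no between-arm test, and the DSMB analyses in 9.1.4 are by total, Node and CTP population. A false harm signal is therefore an inference about how the data would be read. Any by-arm table would still carry the imbalance.

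CRF specifications are issued separately by the lead node's data center (15.1), so a source field may already exist. Sections 9.1.2 and 11.7 do not mention one.

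Therapist reporting protects participants and is not an error. Over-detection in SSB is also the cautious direction for safety. Both points argue against discarding session reports; neither argues against labelling them.

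A reader might infer that SSB has five sessions on partner violence and that its event rate is raised by ascertainment alone. The protocol does not support this. Session 1 carries the HE content, sessions 2 to 4 carry the emphasis, and session 5 reviews handouts. Nothing in the protocol shows that an excess will occur or that it would be wholly artefact.

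**Conclusion.** The concern holds as a possibility built into the design: SSB's recorded adverse event rate and maximal severity can be inflated by unequal ascertainment, and the protocol text provides no means of seeing whether they are. The contact imbalance (five sessions against one, 7.5 to 1 in minutes) is fixed by the protocol. Its effect on counts is not known. The ratios of about 1.0 to 1.4, and up to about 1.6 if events arise after session 1, rest wholly on assumed worksheet detection of 50–100% and disclosure of 5–20% per session. The primary efficacy analysis is not affected. The point deserves action because the source of an event cannot be recovered later if it is not collected.

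**What to change.** - Add a source field to the AE Log and AE CRF: worksheet, therapist or session, other spontaneous report.
- In 11.7, state that any by-arm summary is given for all events and also separately for worksheet-elicited and spontaneously reported events. The worksheet-elicited table is the like-for-like comparison. It stands beside the all-event table and does not replace it, because restricting to the worksheet would drop genuine reports of partner abuse.
- Leave reporting and follow-up of all events unchanged.
- Reconcile section 8.5 with Table 2 on whether abuse is assessed at the immediate post-intervention visit.

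The cost is one data field and one extra table.

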### **9.1.3 Procedures For Human Subject Protection**

The Lead Investigator and Protocol PIs will obtain IRB approval to conduct the study. Any amendments must also receive IRB approval. IRB approval must also be obtained for recruitment, advertising or educational materials. The NIDA CTN DSMB, Long Island Node Quality Assurance Committee representatives, and the participating Node Quality

Assurance representatives will have access to facilities and records for review and verification. For additional protection of confidentiality, the Long Island Node will apply for a NIH Certificate of Confidentiality for the study.

The study assessments and interventions consist of techniques that have been widely used in similar forms with comparable populations with minimal problems for the subjects. Previous research experience suggests that subjects generally perceive these discussions positively. There is, however, some risk that discussing sensitive topics, especially HIV risk behaviors, drug use, sexuality, and intimate relationships, will cause distress or emotional fatigue in some subjects. Yet, these risks do not exceed those that are a normal part of any clinical interview or treatment session. The use of individual assessment procedures has not been shown to be either harmful or directly helpful to substance using/psychiatric patients. Appropriate breaks will be given in the interview or session; if necessary, support will be provided during, or at the end of the interview or session.

All research assistants and therapists will be trained to identify signs of emotional distress, partner abuse, and crisis, and to provide crisis intervention and referral for such situations. A detailed manual will provide ongoing guidance in the standard crisis intervention practices of the CTP. The Site Coordinator and/or Study Clinician will be available by beeper (or other similar method), within 24-hours for consultation and crisis intervention. Should this be needed, he/she will notify the CTP staff members and initiate the clinical procedures that constitute the standard crisis intervention practices of the CTP.

During the course of assessment or intervention, it is possible that a subject may report unprotected (sexual or drug use) risk behavior with an HIV serodiscordant partner. For the protection of the health of the subject and/or her partner, HIV risk and prevention education must be provided to the subject, in accord with both CTP standard practice and local public health law. It is also possible that a subject may newly report HIV seropositivity. We will refer the subject for immediate counseling with the CTP staff member responsible for providing HIV education, making HIV service referrals and satisfying HIV public health policy requirements, in accord with CTP standard practice; through this person, responsibilities for HIV disclosure to state registries and/or partner notification will be met. It is also possible that a subject may report pregnancy. Referrals to appropriate local HIV testing and counseling, partner notification, primary care and/or obstetrical/gynecologic services, in accord with CTP standard practice will be provided.

#### **9.1.4 Data Safety and Monitoring Board**

The CTN DSMB will monitor this trial, in accord with its SOP. The CTN DSMB will conduct adverse event analyses to determine the acceptability of the safety of the trial. Analyses will be conducted for the total population, total Node population, and total CTP population. All informed consent forms and inclusion/exclusion criteria for all subjects will be reviewed. All research records (e.g. case report forms, source documents, etc.) for subjects experiencing SAEs will be reviewed. Per QAS policy, 100% of the research records for the first 10 subjects and a random 10% of the remaining subjects will be reviewed. At each monitoring visit to a CTP, the randomization process will be reviewed to ensure that the randomization is occurring according to protocol procedures.

The CTN DSMB will review demographic characteristics of subjects in each intervention condition – to determine the efficacy of the randomization procedures. The CTN DSMB will review recruitment and retention data to determine the feasibility of the trial. Interim analyses of primary and secondary outcome data will be conducted for the purpose of determining futility of continuing the study, as planned. Our proposed plan for interim analysis is described in section 11.8.

